### General Physical Examination Findings

At screening for inclusion into the study, any clinically significant abnormality should be recorded as a preexisting condition and reported on the Demographics eCRF. From the time of consent forward, any new clinically significant findings or abnormalities that meet the definition of a protocol defined AE must also be recorded and documented as an AE.

### Adverse Event Reporting Period

The study period during which AEs must be reported is normally defined as the period from the initiation of any study procedures to the end of the study treatment follow-up. The start of study procedures is considered to be the point of consent. Any AEs which fit the protocol defined reportable events must be reported from the time of consent until study completion.

At each contact with the subject the investigator must seek information on AEs by specific questioning and, as appropriate, by examination. Information on protocol defined AEs should be recorded immediately in the source document and also in the appropriate AE module of the eCRF. All clearly related signs, symptoms and abnormal diagnostic procedure results should be recorded in the source document and grouped under one diagnosis, as appropriate. The clinical course of each event should be followed until resolution or until it is determined at the end of the study that the AE will not resolve.

#### 8.2 General Adverse Event Definitions

Following is a list of general AE definitions. For the purposes of this study, only SAEs, excluding elective procedures, as well as all AEs related to the operative site should be reported.

#### Adverse Event

An **AE** is any untoward medical occurrence in a clinical investigation subject, which changes the medical baseline of the subject. An AE can be an unfavorable and unintended sign, symptom or disease, whether or not related to the study device (AEs may also be referred to as complications). See Section 8.1, Reporting of Adverse Events, for the AE reporting requirements for this study.

### Anticipated Adverse Event

An **anticipated AE** is an AE, of which the nature, severity or degree of incidence is known and identified in applicable product labeling, published literature or the study protocol. The list of anticipated events is provided in Section 12, Risk/Benefit Assessment.

#### Serious Adverse Event

A **SAE** meets one or more of the following definitions:

- Resulted in in-patient hospitalization
- Resulted in prolonged existing hospitalization
- Resulted in persistent or significant disability/incapacity
- Resulted in permanent impairment of a body function or permanent damage to a body structure
- Necessitated medical or surgical intervention to preclude permanent impairment of a body function or permanent damage to a body structure
- Was a life-threatening situation
- Resulted in patient death

Elective procedures meeting the definition of an SAE do not need to be reported as AEs according to this study protocol.

#### Adverse Device Effect

An **adverse device effect** (ADE) is a negative change in the subject's health that may have been caused by, or associated with, the use of the device.

#### **Unanticipated Adverse Device Effect**

An unanticipated adverse device effect (UADE) is any serious adverse effect on health, safety or any life-threatening problem or death caused by, or associated with, a device if that effect is a problem or death not previously identified in nature, severity or degree of incidence, or any other unanticipated serious problem associated with a device and related to the rights, safety or welfare of subjects.

# 8.3 Study Sponsor Notification by Investigator

Of reportable AEs, certain events must be submitted to Stryker within 24 hours for timely notification:

### Adverse events that require time sensitive reporting:

An adverse event should be reported to the study sponsor (CSM or CSA) either by telephone/fax/email within 24 hours of the site's becoming aware of the event if any of the following apply:

- The AE is considered by the investigator to be device related or if the investigator is uncertain regarding the device related assessment;
- The AE required a reoperation of the study hip or a revision of any study hip components.

An AE eCRF must be completed by the investigator within 24 hours. If a SAE occurs, the de-identified source documentation must be uploaded to the Subject Binder of Stryker's Electronic Data Capture (EDC) system, NetRegulus, within 24 hours of the investigative center's SAE awareness. See Section 11, Data Management, for additional details of Stryker's EDC system. These reports will be evaluated by Stryker to determine if a Product Experience Report (PER) is required.

It is recommended that all other reportable adverse events are reported on eCRFs and submitted to Stryker within 2 weeks.

At the time of the initial report, the following information should be provided:

Subject number	
 
Whether study treatment was
 

 
A description of the event
 
	discontinued
Date of onset	
 
Investigator assessment of the
 

Current status	association between the event and
	the study treatment

# 8.3.1 Ethics Committee/Institutional Review Board Notification by Investigator

Reports of AEs (including follow-up information) must be submitted to the EC or IRB according to their specific requirements. Copies of each report and documentation of EC/IRB notification and receipt will be kept with the investigator's study files.

### 8.4 Recording of Adverse Events

All protocol defined AEs occurring during the study period must be recorded; this includes events that occur between visit intervals. The clinical course of each event should be followed until resolution or stabilization.

### 8.5 Medical Monitoring

It is the responsibility of the investigator to oversee the safety of the study at his/her center. This safety monitoring will include careful assessment and appropriate reporting of AEs, as previously noted. Stryker will conduct formal investigations via the Product Surveillance Department of those AEs which are submitted through our PER System.

# 9 Statistical Plan

# 9.1 Efficacy

# 9.1.1 Primary Efficacy Parameters

The primary efficacy parameter is femoral head dislocation for any reason at 10 years postoperative.

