### 1.1 Background

THA is one of the most clinically successful and cost-effective interventions in health care. Numerous surgeons have reported excellent long-term results in terms of reducing pain, improving function and QOL in patients with debilitating hip disease.

The concept of dual mobility was first defined by [name] in 1976 at the University Hospital of St. Etienne, France. This concept combines Charnley's low friction principle and the McKee-Farrar theory, implanting a large diameter femoral head to decrease the potential for instability. In the dual mobility system, the outer diameter (OD) of the mobile acetabular insert acts as an effective femoral head. The dual mobility system consists of a cementless metallic acetabular shell and a polyethylene insert which freely rotates within the shell and positively captures a prosthetic femoral head. The polyethylene insert functions like a bipolar head. Thus, there are two distinct articulations sharing the same center of motion. See Figure 1 for a representative schematic.

[figure not shown]

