#### **Lever Out/Push Out Testing**

Testing was performed on the worst case component of each material insert to compare the dislocation resistance of the inserts by characterizing their lever out and pull out strengths. The following smallest and thinnest available components were identified as the worst case from each material: X3® part number 1236-2-846 (28 mm ID/ 46 mm OD) & Duration® part number 1235-2-246 (22.2 mm ID/ 46 mm OD). Seventeen test samples were used for each material in both lever-out and pull-out tests. The results of the testing showed that the lever-out and pull-out resistance strengths of the worst case X3® Acetabular Insert were not less than the worst case Duration® Acetabular Inserts, meeting the test acceptance criteria. Ease of use with instrumentation was also identified to be similar between the X3® and Duration® Acetabular Inserts. Refer to test reports TR09-1014, entitled Comparative Lever-Out & Axial Pull-Out Testing of Restoration® ADM X3®, for detailed methods and results.

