### 7.4 Annual Follow-up Visits

Clinical data will be collected via office visit by the investigator at the following annual postoperative intervals: 1-year, 2-year, 3-year, 4-year and 5-year. Tools for postoperative evaluation will be the HHS, AP pelvis, AP femur and lateral radiographs. Radiographs will also be obtained at 1 year and then annually to 5 years postoperatively.

Patient outcomes data will also be collected with the required SF-12, LEAS, and EQ-5D patient questionnaires at each annual visit at the 1-year through 5-year follow-up visits.

All clinical data, radiographs, and patient outcomes data must be collected within  $\pm$  2 months of the 1-year and 2-year anniversary dates. For remaining annual time points, the window expands to  $\pm$  3 months of the 3-year anniversary date and  $\pm$  4 months of the 4-year through 10-year anniversary dates.

The initial phase of the study will continue for 5 years after surgery and include collection of the previously described radiographs, HHS, SF-12, LEAS and EQ-5D patient questionnaires. In the second phase of the study, all subjects will complete a brief Follow-up Questionnaire annually at the 6-year, 7-year, 8-year, 9-year and 10-year follow-up intervals. This form may be completed by the SC during a subject telephone interview, or by the subject either at home or during a clinic visit. The questionnaire will be used to obtain the following information, at a minimum:

- Subject satisfaction with the hip replacement
- Presence of any pain in the study hip
- Any surgeries performed on the study hip
- Any dislocations in the study hip

The questionnaire will also provide information on any revisions and enable calculation of the Kaplan-Meier Survival Curve necessary to meet the primary endpoint of the study.

Additionally, at investigational sites that choose to continue collecting clinical and radiographic data during the second phase of the study, subjects will be evaluated again at 7 and 10 years after surgery.

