### 9.1.4 Primary Efficacy Analysis

A case success is defined as no incidence of postoperative femoral head dislocation within 10 years. A 90% confidence interval of the success rate will be computed at 10 years postoperative. If the lower bound of this confidence interval is greater than 93.5%, the non-inferiority hypothesis will be supported. If the lower bound of this confidence interval is above 97%, the superiority hypothesis will be supported. The Kaplan-Meier survival curve of femoral head dislocation for any reason will also be displayed using SAS/PROC LIFETEST.

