| Deep Joint Infection                                                          | O Iliopsoas Tendon Impingement                                                   | 

Trochanteric Bursitis

          |  |  |
| Device Allergic Reaction                                                      | 

Intra-Prosthetic Dislocation

                                   | 

Trochanteric Crack / Fracture

  |  |  |
| Femoral Bearing Head Crack / Fracture                                         | Nerve Palsy                                                                      | 

Trochanteric Non-Union

         |  |  |
| Femoral Component Loosening                                                   | Osteolysis                                                                       | 

Wound Hematoma

                 |  |  |
| Femoral Component Subsidence                                                  | Reflex Sympathetic Dystrophy (RSD)                                               | Other (Specify)                                  |  |  |
| Femoral Head Dislocation                                                      | г                                                                                | Adverse Event Code                               |  |  |
|                                                                               | Adverse Event Description                                                        |                                                  |  |  |
|                                                                               |                                                                                  |                                                  |  |  |
| B. SYSTEMIC EVENTS                                                            |                                                                                  |                                                  |  |  |
|                                                                               | O Pulmonary Embours  closkeletal (Specify) Respiratory (Specify) Thrombophlebiti | cify) Urogenital (Specify)                       |  |  |
| C. WHEN DID THE EVENT OCCUR?                                                  | ○ Pre-Op ○ Intra-Op                                                              | O Post-Op                                        |  |  |

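### Does the primary endpoint leave open whether an intra-prosthetic dislocation counts as a failure?

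*Combined protocol and SAP*

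**What the plan says.** Section 9.1.1: "The primary efficacy parameter is femoral head dislocation for any reason at 10 years postoperative". Section 9.1.4 turns this into a case rule: "A case success is defined as no incidence of postoperative femoral head dislocation within 10 years". The synopsis hypothesis, the primary objective, section 2.1.1, section 9.1.3 and the sample size section 9.4.2 all name the same event.

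The adverse event form in Appendix F lists "Femoral Head Dislocation" and "Intra-Prosthetic Dislocation" as separate operative-site events and tells the site to check one event. The intra-prosthetic term appears nowhere else in the documents.

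For years 6 to 10, section 7.4 has the follow-up questionnaire ask about "Any dislocations in the study hip", and says that the questionnaire will "enable calculation of the Kaplan-Meier Survival Curve necessary to meet the primary endpoint of the study".

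Two background passages bear on the vocabulary. Section 1.1 says that the outer diameter of the mobile insert "acts as an effective femoral head". The preclinical section describes a bench test done "to compare the dislocation resistance of the inserts by characterizing their lever out and pull out strengths".

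**The concern.** A dual mobility cup has two articulations. The insert can leave the shell, or the femoral head can leave the insert. The form separates these events, but section 9 does not say whether the second is a primary failure.

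Three features seem to keep a wider reading open. The late questionnaire asks about dislocation without type and is said to serve the primary endpoint. The bench section uses the word dislocation for what looks like the head being levered or pulled out of the insert. Section 9.2.1 ties groin pain to a named form field, but the primary endpoint has no such link.

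Few failures are allowed, so if the reading were open, it could be settled after the events were known. In an open-label study managed by the sponsor, that choice could decide either primary conclusion.

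**Working it through.** **Does the text support two readings?**

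- *Name.* The endpoint's name matches one box on the form, and the intra-prosthetic event has its own box. With one event per form, the two do not overlap.
- *Cause.* The phrase on any reason in 9.1.1 concerns why the dislocation happened. It does not widen the type of event.
- *Questionnaire.* A patient cannot say which articulation failed, so the question has to be general. Section 8.1 and the coordinator instruction on the questionnaire send the answer to the coordinator, who completes the adverse event form, and the type is recorded there. The sentence in 7.4 about the survival curve opens with revisions and says nothing about dislocation type.
- *Bench test.* Preclinical wording does not define a clinical endpoint. Even if dislocation covers both articulations in general, the endpoint is the narrower femoral head event.
- *Groin pain.* Section 9.2.1 gives a form field for groin pain, which has no box of its own. It gives none for psoas impingement, which has a near-identical box. Leaving the primary endpoint unmapped fits that pattern.

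**How much could the reading matter?**

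The inputs from 9.1.4 and 9.4.2 are 274 cases, a 97% reference, a 3.5-point margin (threshold 93.5%), and a one-sided 95% lower bound. Power and interval method are not stated. I assume 80% power to reproduce the plan's figure and an exact bound for the rest.

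1. *Plan's figure.* n = [(1.645·√(0.935·0.065) + 0.842·√(0.97·0.03)) / 0.035]² = 246.1. With continuity correction, (246.1/4)·[1 + √(1 + 2/(246.1·0.035))]² = 273.9, so 274. Then 274/0.80 = 342.5, so 343. Both figures reproduce.

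2. *Failures allowed.* The exact lower bound with x failures is BetaInv(0.05; 274 − x, x + 1).

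| Failures | Lower bound | Verdict |
|---|---|---|
| 10 | 93.89% | non-inferiority met |
| 11 | 93.44% | not met |
| 3 | 97.19% | superiority met |
| 4 | 96.69% | not met |

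3. *Chance that the two readings disagree.* Let k be the number of intra-prosthetic cases (assumed) and X ~ Bin(274 − k, p) the like-named failures. With limit L the verdicts differ when L − k < X ≤ L.

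| Test | p | k = 1 | k = 2 | k = 3 |
|---|---|---|---|---|
| Non-inferiority, L = 10 | 3% | 10.5% | 23.3% | 37.3% |
| Non-inferiority, L = 10 | 1% | 0.04% | 0.18% | 0.6% |
| Superiority, L = 3 | 3% | 2.4% | 3.4% | 3.7% |
| Superiority, L = 3 | 1% | 22.2% | 46.7% | 64.7% |

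A Wilson bound allows 11 failures for non-inferiority, and the 3% row becomes 7.8%, 18.1% and 30.8%.

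Each large figure needs a particular like-named rate plus extra events. At 3%, superiority is rarely in reach (3 or fewer failures in 274 has probability 3.5%). At 1%, non-inferiority is almost certain under either reading.

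4. *Cost of the wider reading.* If both boxes counted and intra-prosthetic events came on top of the planned 3%, the chance of meeting non-inferiority would fall from 79.6% to 63.5% with an added 0.5%, or 46.2% with an added 1.0% (both added rates assumed). The like-named reading leaves the planned power unchanged.

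**The case for a change.** The strongest case for a change is that a primary endpoint should be tied to its data source in writing, above all for a device with two articulations and a form that separates two kinds of dislocation. Section 1.1 can be read either way, since the insert serves as the effective head and also captures the real one. Adverse event tables would disclose intra-prosthetic events but would not fix the primary verdict. A sentence would cost almost nothing, and at a 1% like-named rate the superiority verdict could depend on it.

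Part of this stands. Section 9 has no such sentence, and the arithmetic is right. What does not stand is that the reading is open. Counting the intra-prosthetic box would mean adding an event that the endpoint does not name, and section 9.2.2 would show that event separately, with its rate and confidence interval. A reader could recount in a minute.

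Aligning the definition with the literature behind the 97% does not help either, because the documents do not say which events that figure counts. Whether a case stays in the analysis set after revision and termination (sections 9.4.4 and 10.3) is a separate question from which box counts.

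**Conclusion.** The concern does not hold as a reason to change the plan. It identifies a gap in detail that an analyst would fill in one way: the primary failure is the box bearing the endpoint's name, and intra-prosthetic dislocations are reported beside it. Followed as written, the plan has a defined endpoint, and no error in design, sample size or analysis is shown.

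The possible effect ranges from under 0.1% to about 65% disagreement between verdicts, depending on which test is considered, an assumed like-named rate of 1% or 3%, and 1 to 3 assumed intra-prosthetic cases. It also assumes 274 analysed cases and an exact bound. The documents supply no intra-prosthetic rate, so neither the size nor the direction of any bias can be established. A confirming sentence would do no harm, but nothing in the plan's conclusions depends on it.

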# 9.1.2 Secondary Efficacy Parameters

The secondary efficacy parameters are:

- o HHS at each visit, as applicable
- SF-12 at each visit, as applicable
- LEAS at each visit, as applicable
- EQ-5D at each visit, as applicable
- Follow-up Questionnaire annually in postoperative years 6-10

### 9.1.3 Primary Efficacy Hypothesis

The null hypothesis,  $H_0$ , is that the success rate, defined as absence of postoperative femoral head dislocation, at 10 years postoperative is less than  $\delta$ . The alternative hypothesis,  $H_a$ , is that the success rate at 10 years postoperative is greater than or equal to  $\delta$ . When  $\delta$  = 93.5%, the hypothesis is a test for non-inferiority. When  $\delta$ =97%, the hypothesis is a test for superiority.

 $H_0$ :  $p < \delta$ 

 $H_a: p \ge \delta$ 

### 9.1.4 Primary Efficacy Analysis

A case success is defined as no incidence of postoperative femoral head dislocation within 10 years. A 90% confidence interval of the success rate will be computed at 10 years postoperative. If the lower bound of this confidence interval is greater than 93.5%, the non-inferiority hypothesis will be supported. If the lower bound of this confidence interval is above 97%, the superiority hypothesis will be supported. The Kaplan-Meier survival curve of femoral head dislocation for any reason will also be displayed using SAS/PROC LIFETEST.

# 9.1.5 Secondary Efficacy Analysis

A two-sided 0.05 alpha level will be used.

A paired t-test will evaluate the changes in clinical outcomes (HHS, SF-12 and LEAS) preoperative to 10 years postoperative within the Restoration® ADM X3® Acetabular System group, when data is available. In addition, the mean scores (HHS, SF-12 and LEAS) over time will be tabulated, with standard deviation and 95% confidence intervals presented, if applicable.

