#### CONFIDENTIAL

# **Study Synopsis**

	A prospective, post-market, multi-center evaluation of the clinical			
	outcomes of the Restoration® Anatomic Dual Mobility (ADM) X3®			
Title	Acetabular System with Long Term Data Collection for the Accolade®			
	II Hip Stem			
Short Title Restoration® ADM X3® Study				
Protocol Number	70			
Phase	Post-market			
	This study is a prospective, open-label, post-market, non-			
	randomized, multi-center, clinical evaluation of the Restoration® ADM			
	X3 ® Acetabular System for primary total hip arthroplasty (THA) with a			
	cementless application in a consecutive series of patients who meet			
	the eligibility criteria. The total enrollment goal for the study is 350			
Methodology	cases, all of which will receive the Restoration® ADM X3® Acetabular			
	System. A minimum of 100 cases (within the study population) will			
	receive the Accolade® II Hip Stem. The remaining cases will receive			
	any other compatible Stryker femoral component.			
	Data in the literature from other primary hip systems and similar dual			
	mobility cups will be used as historical references.			
	Follow-up of each primary THA case to 10 years			
Study Duration	2. Enrollment period of 24 months			
-	3. Approximate 12-year total duration			
Study Center(s)	Up to 12 investigational centers			

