#### Secondary:

- To evaluate all-cause revision and removal rates in the Restoration® ADM X3® Acetabular System and compare with those reported for other primary hip systems in the literature.
- To compare function and health related quality of life (QOL) between the Restoration® ADM X3® Acetabular System and published results for other primary hip systems. The following outcomes measures will be used for this comparison:
  - Harris Hip Score (HHS)
  - Short Form-12 (SF-12)
  - Lower Extremity Activity Scale (LEAS)
  - o EQ-5D

1-year, 2-year, 3-year, 4-year and 5-year HHS, SF-12 and LEAS will be compared to literature control with respect to improvement from preoperative scores. The EQ-5D data will be summarized and presented.

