#### Secondary:

- The Kaplan-Meier survival curve of revision/removal for the Restoration® ADM X3® Acetabular System (acetabular shell and insert) will be displayed.
- A paired t-test will evaluate the changes in clinical and patient outcomes (HHS, SF-12, EQ-5D, and LEAS), preoperative to 5 years postoperative within the Restoration® ADM X3® Acetabular System (acetabular shell and insert) group, when data is available. In addition, the mean scores (HHS, SF-12, EQ-5D, and LEAS) over time will be tabulated, with standard deviation and 95% confidence intervals presented, if applicable.
- The AE rates and radiographic data will be listed and tabulated at 10 years postoperative for the Restoration®
   ADM X3® Acetabular System group, with 95% confidence intervals presented, if applicable.

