#### **Patient Outcomes:**

Pain, function and health related QOL will be compared between the Restoration® ADM X3® Acetabular System and reports in the literature for other primary THR systems and similar dual mobility cups on the market. The SF-12 is a 12 item patient self-assessment evaluating health and general well being. The LEAS is a tool that has been developed and validated to evaluate the level of patient activity. The EQ-5D is a standardized instrument for use as a measure of health outcome. These tools will be used to assess patient health-related QOL and will be collected preoperatively at the 6-week, 1, 2, 3, 4, and 5-year visits.

A Follow-Up Questionnaire will be administered annually in postoperative years 6-10 to assess patient satisfaction and pain, and to capture AEs. This questionnaire will provide the survivorship information necessary to evaluate the primary objective of the study. Patient outcomes data will also be obtained at the 7-year and 10-year time points at investigational sites that choose to bring their subjects back in for these optional visits, in addition to the required Follow-Up Questionnaire described.

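### The plan promises to compare 1- to 5-year improvement in HHS, SF-12 and LEAS with a literature control, but its only test for these scores is a within-group paired t-test, and no reference improvement is fixed

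*Combined protocol and SAP*

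**What the plan says.** **The objective.** Under the synopsis secondary objectives, the 1- to 5-year "HHS, SF-12 and LEAS will be compared to literature control with respect to improvement from preoperative scores". EQ-5D is listed among the instruments, but its data are only to be summarised. Section 2.1.2 repeats a literature comparison of function and quality of life without naming those years. Its Patient Outcomes text says: "Pain, function and health related QOL will be compared between the Restoration® ADM X3® Acetabular System and reports in the literature". The years given there are the collection schedule.

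**The comparator.** It is described only generically. The synopsis objective refers to other primary hip systems. The Patient Outcomes text widens this to "reports in the literature for other primary THR systems and similar dual mobility cups on the market", as does the synopsis methodology.

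**The analysis.** Section 9.1.5 sets the level ("A two-sided 0.05 alpha level will be used") and names one test: "A paired t-test will evaluate the changes in clinical outcomes (HHS, SF-12 and LEAS) preoperative to 10 years postoperative within the" study group. It adds that "the mean scores (HHS, SF-12 and LEAS) over time will be tabulated, with standard deviation and 95% confidence intervals presented", where applicable. The synopsis statistical section has a different horizon and one more instrument: "A paired t-test will evaluate the changes in clinical and patient outcomes (HHS, SF-12, EQ-5D, and LEAS), preoperative to 5 years postoperative". Section 9.4.1 promises tabulated statistical comparisons for important variables but names neither comparator nor method.

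**The contrast.** For dislocation, Sections 9.1.3, 9.1.4 and 9.4.2 fix a literature value (97%), a margin (3.5%) and a decision rule. No source, selection rule, reference mean, SD, N or margin is given for HHS, SF-12 or LEAS.

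**The concern.** The objective asks whether patients improve as much as patients with other hip systems. The planned test asks whether they improve at all. Its null value is zero change, so no result from it can bear on the first question.

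If the plan is followed as written, the comparative objective has no analysis. A significant paired test could then be presented as if it supported comparability. The study is single-arm and open-label, and Section 16 anticipates publications at 2, 5 and 10 years. Three scores at five annual visits make 3 × 5 = 15 comparisons with no fixed reference, and the class of comparator is itself described in two ways. That leaves room for selective comparison.

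**Working it through.** **1. The plan's own figures.** The documents give no sample size, SD or reference for the scores. The only stated sample size is for dislocation. Taking 97% against 93.5%, one-sided 0.05, and 80% power (an assumption, since power is not stated):

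- n = [(1.645·√(0.935×0.065) + 0.842·√(0.97×0.03)) / 0.035]² = 246.1
- with continuity correction, 246.1/4 × (1 + √(1 + 2/(246.1×0.035)))² = 273.9, so 274
- enrolment after 20% loss: 274/0.80 = 342.5, so 343

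These match Section 9.4.2. They suggest what n might be available for the scores: 274, or 350 × 0.80 = 280. Both are assumptions here, because the figures were derived for another endpoint.

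**2. How little change the paired test needs.** In units of the SD of the change, the test at two-sided 0.05 is significant once the observed mean change exceeds t(0.975, n−1)/√n. It has 80% power at about (1.960 + 0.842)/√n.

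| Evaluable pairs (assumed) | Significant above | 80% power at |
|---|---|---|
| 100 | 1.98/10.00 = 0.198 SD | 2.802/10.00 = 0.280 SD |
| 274 | 1.97/16.55 = 0.119 SD | 2.802/16.55 = 0.169 SD |
| 280 | 1.97/16.73 = 0.118 SD | 2.802/16.73 = 0.167 SD |

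The row for 100 matters for the 10-year test in Section 9.1.5. The evaluation schedule makes these scores optional at 7 and 10 years, so n there is unknown and could be well below 274.

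**3. Illustration (assumed values).** Suppose the literature improvement is 1.0 SD and the device truly gives half of it, 0.5 SD.

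- Test against zero: the expected t is about 0.5 × √100 = 5.0 with 100 pairs and 0.5 × √274 = 8.3 with 274. By the noncentral t distribution, the probability of rejecting zero is 0.9986 and above 0.999.
- 95% interval set against the 1.0 SD reference, treated as known: the probability that it lies wholly below is about Φ(0.5·√n − 1.96). With 100 pairs this is Φ(3.04) = 0.9988, and with 274 it is higher still.

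The planned test declares success almost every time, in the same data where a comparison with the reference would show the shortfall almost every time.

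**4. What a real comparison could deliver.** Against a fixed reference, the 95% half-width is the middle column of the table: 0.20 SD with 100 pairs and 0.12 SD with 274. If the reference carries its own error, the half-width is 1.96·√(1/n + 1/m), for reference size m and an equal SD (both assumptions). With n = 274 and m = 100 this is 1.96·√(0.00365 + 0.01000) = 0.23 SD. With m = 274 it is 1.96·√(2/274) = 0.17 SD. No absolute figure in score points is possible, because the documents give no SD of change.

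**The case against.** The strongest reply is that this is a single-arm post-market study. The scores carry no hypothesis, margin or success criterion, so a descriptive comparison with published series is a fair reading of the objective. Tabulated means with 95% confidence intervals are what a reader would set beside such series. Part of this stands: a formal test is not required, and rewording the objective as descriptive would be a legitimate cure. It does not remove the mismatch, because the tabulated intervals are for scores whereas the objective concerns improvement, and no reference is given to set them against.

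A second reply is that the arithmetic shows a general property of paired tests under assumed n and SDs. That is true of the sizes. The conclusion does not depend on them, since no test against zero can establish parity with a non-zero reference.

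A reader might infer that the sponsor will, or must, choose the comparator after seeing the results. The documents do not say so: they leave the literature control generic and are silent on when sources are selected. What they support is only that nothing prevents a late choice. A reader might also take Section 2.1.2 as promising comparisons at each of years 1 to 5. Only the synopsis does that.

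**Conclusion.** The concern holds. The plan states a comparative objective for improvement in HHS, SF-12 and LEAS at years 1 to 5 and provides no analysis that can answer it. Assuming 274 to 280 evaluable pairs, the paired test is significant once the mean change exceeds about 0.12 SD of the change; with 100 pairs the threshold is about 0.20 SD. Significance is therefore compatible with a device giving half the reference improvement.

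The test's horizon also needs reconciling: 10 years in Section 9.1.5, 5 years in the synopsis, and years 1 to 5 in the objective. The consequence is limited to secondary conclusions. The dislocation analysis has its own fixed reference and is untouched by this point.

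**What to change.** In both Section 9.1.5 and the synopsis statistical section:

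- Label the paired t-test as descriptive. Reconcile the 5- and 10-year horizons with the year 1 to 5 objective, and settle whether EQ-5D is included.
- Before the score data are next analysed, state the criteria for selecting literature series, including whether dual mobility cups count. By those criteria, fix a reference mean improvement, with its SD, N and visit, for each of HHS, SF-12 and LEAS at each of years 1 to 5 where a published value exists.
- Report the study mean improvement with its 95% confidence interval, and the difference from the reference with an interval that also carries the reference's standard error. Note that case-mix may differ from the historical series.
- Where no suitable reference exists, or if the sponsor will not commit to one, reword that objective as descriptive change from baseline and make no comparative claim.

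The cost is revised wording and a short literature extraction, with no new data and no change in sample size. The documents do not show whether usable published changes exist for every score and visit, which is why the descriptive fallback is needed. The downside for the sponsor is being bound to a comparator chosen in advance.
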